11.5.4 Exploratory Pharmacokinetic Analyses

In all patients with at least one PK sample collected, the trough plasma rucaparib PK data (C_{min}) and summary statistics (N, mean, SD, minimum, median, max, CV%) will be reported. The PK data and selected safety and efficacy endpoints will be included in exploratory population PK and exposure-response analyses, and the results will be reported separately.

11.6 Safety Analyses

Safety endpoints include incidence of AEs, clinical laboratory abnormalities, and dose modifications.

Data from all patients who receive at least 1 dose of study drug will be included in the safety analyses. AEs, clinical laboratory results, vital signs, ECG results, ECOG performance status, body weight, and concomitant medications/ procedures will be tabulated and summarized.

11.6.1 Adverse Events

AEs will be classified using the Medical Dictionary for Regulatory Activities (MedDRA) classification system. The severity of the toxicities will be graded according to the NCI CTCAE Version 4.03 or later. Only treatment-emergent adverse events (TEAEs) will be collected: TEAEs are defined as AEs with onset date on or after the date of first dose of study drug until the date of the last study drug dose plus 28 days.

The number and percentage of patients who experienced TEAEs for each system organ class (SOC) and preferred term will be presented. Multiple instances of the TEAE in each SOC and multiple occurrences of the same preferred term are counted only once per patient. The number and percentage of patients with at least 1 TEAE will also be summarized.

Separate tables will be presented as follows:

- All TEAEs;
- TEAEs by CTCAE grade;
- Grade 3 or greater TEAEs;
- Treatment-related TEAEs;
- Serious TEAEs;
- TEAEs with an outcome of death;
- TEAEs leading to discontinuation of study medication;
- TEAEs resulting in interruption/delay of study medication; and
- TEAEs resulting in dose reduction of study medication.

The incidence of TEAEs will be summarized by relationship to study drug according to the following categories: “treatment-related,” or “not treatment-related”. If a patient experiences multiple occurrences of the same AE with different relationship categories, the patient will be counted once, as a relationship category of treatment related.

If a patient experiences multiple occurrences of the same AE with different toxicity grades, the patient will be counted once for the maximum (most severe) toxicity grade. AEs with a missing toxicity grade will be presented in the summary table with a toxicity grade of “Missing.” For each toxicity grade, the number and percentage of patients with at least 1 TEAE of the given grade will be summarized.

11.6.2 Clinical Laboratory Evaluations

Clinical laboratory evaluations include the continuous variables for hematology, serum chemistry, and urinalysis. The laboratory values will generally be presented in SI units. The on-treatment period will be defined as the time from the first dose of study drug to 28 days after

the last dose of study drug. Laboratory values collected during the on-treatment period will be included in the summary tables. The laboratory values collected after the on-treatment period will only be presented in the data listings.

The summary of laboratory data will include shift tables based on CTCAE for shifts in grade from baseline to maximum, minimum and last value during the on-treatment period.

Supporting laboratory data including normal ranges and abnormal laboratory flags will be provided using by-patient listings. Separate listings will be produced for clinically significant laboratory abnormalities (ie, those that meet Grade 3 or 4 criteria according to CTCAE).

11.6.3 Vital Sign Measurements

The on-treatment period will be defined as the time from the first dose of study drug to 28 days after the last dose of study drug. Vital sign measurements collected during the on-treatment period will be included in the summary tables. The vital sign measurements collected after the on-treatment period will only be presented in the data listings.

The summary of vital sign data will include descriptive statistics (N, mean, SD, minimum, median, third quartile, and maximum) of the maximum, minimum and last value during the on-treatment period. Summaries using descriptive statistics (N, mean, SD, minimum, median and maximum) of the change from baseline to the maximum, minimum, and last value during the on-treatment period will also be given.

11.7 Interim Analysis

Cohort A

As described in [Section 11.2](#), up to approximately 150 patients will be enrolled in Cohort A, which will be divided into 2 sub-cohorts defined by deleterious gene mutation (BRCA1/2 vs. ATM).

Cohort A (BRCA1/2)

A Simon 2-stage design to evaluate confirmed ORR by modified RECIST Version 1.1 criteria per investigator will be used. With rolling enrollment, after the first 37 patients with a deleterious BRCA1/2 mutation have either: a) completed 16 weeks of treatment, or b) discontinued treatment prior to completing, an interim analysis will be performed (ie, Stage 1). If $\leq 8/37$ patients in Stage 1 have a confirmed objective response (CR or PR per investigator and without progression in bone per PCWG3), the DMC will evaluate the overall benefit/risk for patients with deleterious BRCA1/2 mutations in this cohort and make a recommendation whether further enrollment should be discontinued. If $\geq 9/37$ patients have a confirmed objective response, then enrollment will continue with additional patients in Stage 2. With 83 total patients with a deleterious BRCA1/2 mutation, characteristics of the Simon 2-stage design include:

- 5% probability of accepting a minimally effective drug
- 90% probability of accepting an effective drug

- ORR of 20% for a minimally effective drug
- ORR of 35% for an effective drug

Cohort A (ATM)

A Simon 2-stage type futility rule will be employed in Cohort A (ATM). An interim analysis (Stage 1) will be performed after the first 31 patients have either: a) completed 16 weeks of treatment; or b) discontinued treatment prior to completing. Enrollment into the study will continue while this interim analysis occurs. If $\leq 6/31$ patients in Stage 1 have a confirmed objective response (CR or PR per investigator and without progression in bone per PCWG3), the DMC will evaluate the overall benefit/risk for patients with deleterious ATM mutations in this cohort and make a recommendation whether further enrollment should be discontinued. If $\geq 7/31$ patients have a confirmed objective response, then enrollment will continue in Stage 2. With 53 total patients with a deleterious ATM mutation, characteristics of the Simon 2-stage (minimax) design include:

- 5% probability of accepting a minimally effective drug
- 80% probability of accepting an effective drug
- ORR of 20% for a minimally effective drug
- ORR of 35% for an effective drug

Cohort B

As described in [Section 11.2](#), up to approximately 150 patients will be enrolled into Cohort B which will be divided into 2 sub-cohorts defined by deleterious gene mutation (BRCA1/2 vs. ATM).

Cohort B (BRCA1/2)

A Simon 2-stage type futility rule will be employed in Cohort B (BRCA1/2). An interim analysis (Stage 1) will be performed after the first 19 patients have either: a) completed 16 weeks of treatment; or b) discontinued treatment prior to completing. Enrollment into the study will continue while this interim analysis occurs. If $\leq 4/19$ patients in Stage 1 have a PSA response ($\geq 50\%$ decrease), the DMC will evaluate the overall benefit/risk for patients with deleterious BRCA1/2 mutations in this cohort and make a recommendation whether further enrollment should be discontinued. If $\geq 5/19$ patients have a PSA response, then enrollment will continue in Stage 2. With 54 total patients with a deleterious BRCA1/2 mutation, characteristics of the Simon 2-stage design include:

- 5% probability of accepting a minimally effective drug
- 90% probability of accepting an effective drug
- ORR of 20% for a minimally effective drug
- ORR of 40% for an effective drug

If there are at least 16 responses in 54 patients with a deleterious BRCA1/2 mutation, the null hypothesis (ORR = 20%) will be rejected. Additionally, if the criteria for Stage 2 are met, additional patients, up to approximately 100 total, may be enrolled. Enrollment in Cohort B (BRCA1/2) will be halted when Cohort A (BRCA1/2) is fully enrolled.

Cohort B (ATM)

A Simon 2-stage type futility rule will be employed in Cohort B (ATM). An interim analysis (Stage 1) will be performed after the first 18 patients have either: a) completed 16 weeks of treatment; or b) discontinued treatment prior to completing. Enrollment into the study will continue while this interim analysis occurs. If $\leq 4/18$ patients in Stage 1 have a PSA response ($\geq 50\%$ decrease), the DMC will evaluate the overall benefit/risk for patients with deleterious ATM mutations in this cohort and make a recommendation whether further enrollment should be discontinued. If $\geq 5/18$ patients have a PSA response, then enrollment will continue in Stage 2. With 33 total patients with a deleterious ATM mutation, characteristics of the Simon 2-stage (minimax) design include:

- 5% probability of accepting a minimally effective drug
- 80% probability of accepting an effective drug
- ORR of 20% for a minimally effective drug
- ORR of 40% for an effective drug

If there are at least 11 responses in 33 patients with a deleterious ATM mutation, the null hypothesis (ORR = 20%) will be rejected. Additionally, if the criteria for Stage 2 are met, additional patients, up to approximately 50 total, may be enrolled. Enrollment in Cohort B (ATM) will be halted when Cohort A (BRCA1/2) is fully enrolled

Cohort C

Up to approximately 60 patients will be enrolled into Cohort C. Enrollment in Cohort C will be halted when Cohort A (BRCA1/2) is fully enrolled. Since this cohort will enroll patients that have 1 of several different deleterious HRR gene mutations, each gene will be examined separately. It is anticipated that < 6 patients will have a deleterious mutation in the same HRR gene; however, if enrollment of patients with a deleterious mutation in the same gene is higher than anticipated then enrollment will be held at 6 patients with any 1 deleterious gene mutation and a futility rule will be implemented such that if no responses are observed, then enrollment of patients with a deleterious mutation in that particular gene will be stopped, in consultation with the DMC.

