Note: If the study is to proceed to Stage 2, additional patients with a deleterious BRCA1/2 mutation up to 100 total patients (and a maximum of 60 patients with only measurable lymph node disease) will be enrolled in Cohort A (BRCA1/2) if additional clinical data is requested by the regulatory authorities to support regulatory filing. If sufficient evidence exists to support a regulatory filing prior to fully enrolling Cohort A (BRCA1/2), enrollment may be discontinued early.

Cohort A (ATM)

Patients in Cohort A (ATM), having a deleterious ATM mutation, will be enrolled concurrently with patients from Cohort A (BRCA1/2). It is expected that about 1/3 of the Cohort A patients will have deleterious ATM mutations. If 100 patients are enrolled in Cohort A (BRCA1/2), then approximately 50 patients would be expected to enroll into Cohort A (ATM).

A Simon 2-stage type futility rule will be employed in Cohort A (ATM). An interim analysis (Stage 1) will be performed after the first 31 patients have either: a) completed 16 weeks of treatment; or b) discontinued treatment prior to completing. Enrollment into the study will continue while this interim analysis occurs. If $\leq 6/31$ patients in Stage 1 have a confirmed objective response (CR or PR per investigator and without progression in bone per PCWG3), the DMC will evaluate the overall benefit/risk for patients with deleterious ATM mutations in this cohort and make a recommendation whether further enrollment should be discontinued. If $\geq 7/31$ patients have a confirmed objective response, then enrollment will continue in Stage 2. With 53 total patients with a deleterious ATM mutation, characteristics of the Simon 2-stage (minimax) design include:

- 5% probability of accepting a minimally effective drug
- 80% probability of accepting an effective drug
- ORR of 20% for a minimally effective drug
- ORR of 35% for an effective drug

If there are at least 16 responses in 53 patients with a deleterious ATM mutation, the null hypothesis (ORR = 20%) will be rejected. This design yields a type I error rate of 5% and power of 80% when the true response rate is 35%.

Cohort B

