9.5.5 Study Day 57 (Week 9) and Every 28 Days Thereafter

Patients will be instructed to refrain from taking their first dose of rucaparib at home on study visits when plasma samples are collected for PK.

Plasma samples for PK analysis should be collected before the morning dose on Study Day 57, Day 85, and Day 113 as close to 12 hours after the previous dose as possible. If the start of the next dose is delayed, the PK sample should still be collected during this visit instead of the delayed start of the next study visit;

The following procedures will be completed:

- PRO collected using the BPI-SF ([Appendix 6](#)), FACT-P ([Appendix 7](#)), EQ-5D-5L ([Appendix 8](#)), and analgesic drug score instruments ([Appendix 9](#); should be completed before other procedures)
- Physical examination
- Weight
- Vital signs
- Tumor assessment scans at the end of every 8 calendar weeks (± 7 days) for the first 24 weeks (Weeks 9, 17, 25), and then every 12 calendar weeks (± 7 days) thereafter (Weeks 37, 49, 61, etc)
- Concomitant medications and procedures
- ECOG performance status ([Appendix 3](#))
- PSA measurement
- Hematology

- Serum chemistry (fasting is not required)
- Urinalysis
- Plasma sample for ctDNA
- Plasma sample for PK analyses (Study Day 57, Day 85, and Day 113 only)
- AE (inclusive of SAE and AESI) monitoring
- Dispensation of rucaparib

Patients will ingest rucaparib twice daily at about the same times every day as close to 12 hours apart as possible. Rucaparib should be taken with at least 8 oz (240 mL) of water with or without food. Patients will keep all unused containers (empty, partially used, and/or unopened) and return with them to the study site for accountability at the next visit. In the event of toxicities, re-treatment or dose modification will be according to the criteria described in [Section 7.4.2](#).

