13.6 Data Monitoring Committee

A DMC will be established to review safety data in compliance with a prospective charter. For Cohort A and B, DMC may be requested to evaluate the overall risk/benefit of rucaparib therapy in this patient population based on the outcome of Stage 1 interim analysis. The DMC will be comprised of study investigators and of sponsor representatives. The DMC responsibilities, authorities, and procedures for this study will be documented in the DMC charter, which will be endorsed by the DMC members and signed by the DMC chair prior to the first data review meeting. The DMC will also ensure the study is beneficial to patients (see [Section 11.7](#)).

The DMC will meet after the first 20 patients received rucaparib for at least 28 days or discontinued study treatment, and then at least semi-annually after sufficient data has been collected. The DMC chairperson or sponsor may convene an unscheduled DMC meeting if there are newly identified significant safety concerns. Following data review, the DMC will recommend continuation, revision, or termination of the study and/ or continuing or halting enrollment into a particular subgroup. Details regarding the DMC will be in the committee charter.

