In some circumstances, it may be difficult to distinguish residual disease from normal tissue. When evaluation of CR depends on this determination, it is recommended that the residual lesion be investigated (fine needle aspiration/biopsy) prior to confirming the complete response status.

Confirmation

If an initial CR or PR is noted, confirmatory scans must be performed at least 4 weeks later.

Duration of Response

CT scans are required for this study at screening and every 8 calendar weeks (within 7 days before or after is permitted) thereafter. Patients who have been on study at least 24 weeks, may decrease the frequency of disease/ tumor assessments to every 12 calendar weeks (within 7 days before or after is permitted).

Duration of Overall Response

The duration of overall response is measured from the time measurement criteria are met for CR or PR (whichever is first recorded) until the first date that recurrent or PD is objectively documented (taking as reference for PD the smallest measurements recorded since the treatment started), including progression in bone per PCWG3 criteria.

The duration of overall CR is measured from the time measurement criteria are first met for CR until the first date that recurrent disease is objectively documented.

Duration of Stable Disease

SD is measured from the start of the treatment until the criteria for progression are met, taking as reference the smallest measurements recorded since the treatment started.

PCWG3 Criteria for Assessment of Bone Disease

PCWG3 criteria will be used to document evidence of disease progression in bone lesions as described by Scher, et al. 2016²⁵

Imaging of Baseline Bone Disease

The use of bone scan as the standard for bone imaging is retained in PCWG3, with the presence or absence of metastasis recorded first. A quantitative measure of disease burden, such as lesion number, the bone scan index, or lesion area, is also suggested, recognizing that these measures require further analytical and prospective clinical validation. Changes in lesions considered metastatic on bone scintigraphy should be followed and assessed serially using a bone scan assessment form. Areas/lesions on bone scintigraphy that are suggestive can be assessed further with CT or MRI and followed separately, but such supplemental imaging should not be used to establish indicator lesions for the purposes of a trial.

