2.3 Sample Size Justification

The enrollment planned for this study is approximately 360 patients, with up to approximately 150 patients with measurable visceral and/or nodal disease in Cohort A (ie, up to 100 patients with a deleterious BRCA1/2 mutation [with a maximum of 60 patients who have only measurable lymph node disease], and up to approximately 50 patients with a deleterious ATM mutation); up to approximately 150 patients without measurable disease in Cohort B (ie, up to approximately 100 patients with a deleterious BRCA1/2 mutation and 50 patients with a deleterious ATM mutation); and up to approximately 60 patients with or without measurable visceral and/or nodal disease who have a deleterious mutation in a HRR gene other than BRCA1/2 or ATM in Cohort C.

Cohort A

Cohort A will be divided into 2 sub-cohorts defined by deleterious gene mutation (BRCA1/2 vs. ATM).

Cohort A (BRCA1/2)

A Simon 2-stage design to evaluate confirmed ORR by modified RECIST Version 1.1 criteria per investigator will be used. With rolling enrollment, after the first 37 patients with a

deleterious BRCA1/2 mutation have either: a) completed 16 weeks of treatment or b) discontinued treatment prior to completing, an analysis will be performed (ie, Stage 1). If $\leq 8/37$ patients in Stage 1 have a confirmed objective response (CR or PR per investigator and without progression in bone per PCWG3), the data monitoring committee (DMC) will evaluate the overall benefit/risk for patients with deleterious BRCA1/2 mutations in this cohort and make a recommendation whether further enrollment should be discontinued. If $\geq 9/37$ patients have a confirmed objective response, then enrollment will continue with additional patients in Stage 2. With 83 total patients with a deleterious BRCA1/2 mutation, characteristics of the Simon 2-stage design include:

- 5% probability of accepting a minimally effective drug
- 90% probability of accepting an effective drug
- ORR of 20% for a minimally effective drug
- ORR of 35% for an effective drug

If there are at least 23 responses in 83 patients with a deleterious BRCA1/2 mutation, the null hypothesis (ORR = 20%) will be rejected. This design yields a type I error rate of 5% and power of 90% when the true response rate is 35%.

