10.1 Primary Efficacy Analysis

For Cohort A, the primary efficacy endpoint is confirmed radiographic ORR by central IRR (as described in [Section 9.1](#)) in patients with measurable visceral and/or nodal disease at baseline. To be considered a responder at a specific time point, a patient must have a CR or PR assessment per modified RECIST and no confirmed bone progression per PCWG3 on or prior to a CR or PR. To be considered a confirmed responder, a patient must have at least 2 responses at least 4 weeks apart prior to a modified RECIST/PCWG3 progression event.

Confirmed radiographic ORR will be summarized with frequencies and percentages along with 95% confidence intervals. The frequency and percentages of patients with a best overall response of complete response (CR), partial response (PR), stable disease (SD), or progressive disease (PD) will also be summarized.

An analysis of confirmed radiographic ORR by the investigator will also be conducted as supportive to the primary endpoint and will use the Investigator Efficacy Population (patients evaluable for response by modified RECIST/PCWG3 criteria per investigator).

For Cohort B, the primary efficacy endpoint is confirmed PSA response as assessed by a local laboratory in patients without measurable disease at baseline (by central IRR). Confirmed PSA response is defined as having 2 consecutive PSA values (at least 3 weeks apart) that are at least 50% lower than baseline and that occur prior to PSA progression (as defined in [Section 10.2.6](#)). Per PCWG3, early rises (before 12 weeks following first dose of study drug) in PSA should be ignored when determining PSA response. Confirmed PSA response will be calculated for patients with PSA values at baseline.

Confirmed PSA response will be summarized separately, with frequencies and percentages along with 95% confidence intervals, for patients without measurable disease per IRR (primary endpoint) and without measurable disease per Investigator (supportive analysis). PSA response will also be summarized for patients with measurable disease (both IRR and Investigator, separately) and for all patients.

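### Does taking the Cohort A Stage 1 count at 16 weeks, when only confirmed responses count, make the futility rule unsound?

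*Protocol*

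**What the plan says.** **Trigger.** Protocol 11.7 and the Synopsis time the BRCA1/2 look as follows: "With rolling enrollment, after the first 37 patients with a deleterious BRCA1/2 mutation have either: a) completed 16 weeks of treatment", or have stopped treatment before then. SAP 2.3 and 11.4 repeat it ("discontinued treatment prior to completing, an analysis will be performed (ie, Stage 1"). The ATM look has the same form, with 31 patients.

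**What is counted.** Confirmed CR or PR per investigator, without bone progression. The DMC review is prompted by 8 or fewer of 37 (BRCA1/2) or 6 or fewer of 31 (ATM).

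**Confirmation.** Protocol Appendix 2: "If an initial CR or PR is noted, confirmatory scans must be performed at least 4 weeks later". SAP 10.1: "To be considered a confirmed responder, a patient must have at least 2 responses at least 4 weeks apart".

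**Scan schedule.** Protocol 9.5.5 places scans "for the first 24 weeks (Weeks 9, 17, 25), and then every 12 calendar weeks", each with a window of 7 days either side.

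**Consequence of crossing the bound.** The DMC weighs benefit and risk and is to "make a recommendation whether further enrollment should be discontinued". Protocol 13.6 adds: "The DMC responsibilities, authorities, and procedures for this study will be documented in the DMC charter". That charter is not among the documents reviewed.

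**The concern.** The trigger and the counted event do not fit neatly together. Sixteen weeks of treatment leave time to confirm a response first seen at Week 9, but not one first seen at Week 17. Neither document names a later data cut or says how a response awaiting confirmation is scored.

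If the count were frozen when the last patient reached 16 weeks, such responses in the latest-enrolled patients would be scored as failures. That error runs one way: an effective drug would go to futility review more often than the bounds imply. If the DMC then always stopped enrolment, power would fall below the stated 90% and 80%.

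**Working it through.** **1. The plan's own figures.** With X1 the Stage 1 count, n1 the Stage 1 size, r1 the futility bound and R the final rejection count out of N:

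- Flag probability = P(X1 ≤ r1), with X1 ~ Bin(n1, p).
- Power or type I error = Σ over x > r1 of P(X1 = x) × P(Bin(N − n1, p) ≥ R − x).

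| Sub-cohort | r1/n1, R/N | Type I error at 20% | Power at 35% | Flag at 35% |
|---|---|---|---|---|
| BRCA1/2 | 8/37, 23/83 | 4.87% | 90.09% | 5.88% |
| ATM | 6/31, 16/53 | 4.98% | 80.17% | 4.62% |

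The stated 5%/90% and 5%/80% are reproduced.

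**2. Timing.** Sixteen weeks end on Day 16 × 7 = 112. The Week 17 visit is Day 57 + 28 + 28 = 113, so its scan falls on Days 106 to 120. Adding 28 days gives Day 141 (134 to 148) as the earliest confirmation. Week 25 is Day 113 + 56 = 169. A patient therefore needs about 4 more weeks after the trigger, or 8 if confirmation waits for the scheduled scan.

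**3. Who is affected.** Only patients who entered within the last 4 (or 8) weeks of Stage 1 accrual. The documents give no accrual time, so assume 37 BRCA1/2 patients enter evenly over T = 26 to 52 weeks. Protocol Synopsis: "It is expected that about 1/3 of the Cohort A patients will have deleterious ATM mutations". ATM then accrues at half the BRCA1/2 rate, and 31 patients take T × (31/37) × 2 = 43.6 to 87.1 weeks. Patients short of follow-up, k:

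- BRCA1/2: 37 × 4/52 = 2.8 to 37 × 4/26 = 5.7; for 8 weeks, 5.7 to 11.4.
- ATM: 31 × 4/87.1 = 1.4 to 31 × 4/43.6 = 2.8; for 8 weeks, 2.8 to 5.7.

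**4. Effect.** Let m be the share of eventual confirmed responses first seen at Week 17. It is not in the documents; assume 10 to 20%. The Stage 1 count becomes Bin(n1 − k, p) + Bin(k, p(1 − m)). Missed responses are restored at the final analysis. Power is computed as if every flag stopped enrolment. At p = 35%:

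| Case | k, m | Flag | Above design | Power |
|---|---|---|---|---|
| BRCA1/2, 4-week scan | 3, 10% to 6, 20% | 6.30 to 7.70% | 0.42 to 1.82 points | 89.76 to 88.63% |
| ATM, 4-week scan | 1, 10% to 3, 20% | 4.74 to 5.40% | 0.12 to 0.78 points | 80.13 to 79.88% |
| BRCA1/2, wait for Week 25 | 6, 10% to 11, 20% | 6.75 to 9.55% | 0.87 to 3.67 points | 89.40 to 87.08% |
| ATM, wait for Week 25 | 3, 10% to 6, 20% | 5.00 to 6.28% | 0.38 to 1.66 points | 80.03 to 79.52% |

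Type I error at 20% falls slightly. For BRCA1/2 it goes from 4.87% to 4.82 to 4.63% in the 4-week case.

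**5. Price of waiting.** If the drug is ineffective, holding the look for 4 weeks enrols about 3 to 6 more BRCA1/2 and 1 to 3 more ATM patients. For 8 weeks it is about 6 to 11 and 3 to 6.

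**The case for a change.** The strongest case for a change is that the undercount always runs against an effective drug, that one sentence would settle it, and that leaving the cut to discretion is unattractive in an open-label study whose DMC includes investigators and sponsor representatives. Larger numbers can also be produced. If 20 to 40% of responses are first seen at Week 17 or later and confirmation waits for Week 25, the flag rate reaches 14.7% for BRCA1/2 and 8.3% for ATM, with power of 82.6% and 78.6% if the flag always stops enrolment.

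The direction of the error and the silence on the cut stand. The larger figures do not measure this point. They include first responses at Week 25 or later, which a 4- or 8-week delay would not recover, yet they count only patients lacking 4 or 8 weeks of follow-up. Any look with staggered entry misses some late events.

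A clarifying sentence is also less simple than it seems. One tied to responses on record at 16 weeks would miss most of the intended cases, since the nominal Week 17 scan falls on Day 113. One that stopped waiting at discontinuation would miss patients who leave treatment without radiologic progression, whom Protocol 5.1.4 and 9.9 keep on the scan schedule.

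**Conclusion.** No change is needed. The wording sets the earliest time for the look, so a cut that allows for confirmation already complies. Crossing the bound leads only to a DMC judgement on benefit and risk. SAP 11.4 has that committee reviewing efficacy regularly, and nothing prevents it from seeing responses awaiting confirmation beside the confirmed count. For ATM, enrolment expressly continues during the look. Responses confirmed later count at the final analysis, and type I error is not inflated.

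With a 4-week confirmation scan, the effect on an advisory flag is about 0.4 to 1.8 points (BRCA1/2) and 0.1 to 0.8 points (ATM). If confirmation waits for Week 25, it is at most about 3.7 and 1.7 points. These sizes rest on the assumed accrual time, an assumed 10 to 20% of responses first seen at Week 17, and a true response rate of 35%. Power is lost only if the flag is treated as a stop.

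Against that stands a later look and more patients enrolled on a drug that may not work. Statisticians could reasonably choose either, and the plan's choice of the earlier look leads to sound conclusions.
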